2.1 Primary objectives

- To evaluate the effect of different doses of TIP administered o.d. and one b.i.d. dose on the change in *P. aeruginosa* bacterial load in sputum as assessed by the change in colony forming units (CFUs) from baseline to Day 29 of treatment, each compared to placebo.
- To assess the safety and tolerability with different doses of TIP administered o.d. and b.i.d. and different regimens (TIP and TIP/placebo cyclical) during the treatment epoch (112 days) and during the follow-up epoch (56 days) for each as compared to placebo.

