9.5.2 Safety variables

All safety analyses will be performed using the safety population, and will be presented by treatment groups. Baseline for safety analyses is defined as the last measurement prior to the first dose of study medication in the study.

Appropriate summary statistics will be provided for laboratory test results, audiology, bronchial hyperreactivity and vital signs.

AEs will be deemed treatment-emergent if the onset date is on or after the date of first study drug and until study completion. Treatment emergent AEs will be summarized by MedDRA primary SOC and preferred term for each cycle and overall. The actual MedDRA version in effect at the time of the clinical study report will be used for coding AEs.

Audiology testing will be performed at selected centers and in patients with hearing events. Audiology function data will be analyzed via summary statistics by treatment and visit.

Clinical laboratory parameters will be summarized using means and mean changes from baseline to each post-baseline visit by treatment group. Shift-from-baseline summaries (shift tables) will be presented for the last available measurement (Termination Visit).

Vital sign parameters will be summarized using means and mean changes from baseline by treatment group and visit.

Analysis of post-inhalation events will be conducted for the two types of events (post-inhalation clinical events/post-inhalation adverse events). The number of patients with post-inhalation events will be summarized by treatment. In addition, the number of these events and the event rate adjusted for exposure will be displayed by treatment.

Post-inhalation events occurring at a site visit within 5 minutes (yes/no), post-inhalation events that are ongoing at completion of the site visit (yes/no) and for which an action taken to reduce the event (yes/no), the time-point of an event and the time of onset (≤ 30 sec, >30 sec-1min, >1 -2min, >2 -5min, >5 min) will be summarized with the number and percentage overall and for each cycle. Descriptive statistics including mean, standard deviation, minimum, median and maximum will be provided for the duration of the event in seconds.

[figure not shown]

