The randomization numbers will be generated using the following procedure to ensure that treatment assignment is unbiased and concealed from patients and investigator staff. A patient randomization list will be produced by the IRT provider using a validated system that automates the random assignment of patient numbers to randomization numbers. These randomization numbers are linked to the different treatment arms, which in turn are linked to medication numbers. A separate medication list will be produced by or under the responsibility of Novartis Drug Supply Management using a validated system that automates the random assignment of medication numbers to packs containing the investigational drug(s).

The treatment arms distributed among the 3 cohorts are described below. TIP is supplied in hard capsules at 28mg dosage strength, therefore 3 cohorts correspond to 3 different dose

levels of TIP, i.e., 84mg once a day (o.d.), 140mg o.d. and 112mg twice a day (b.i.d.).

Cohort A: 3 capsules o.d.

- **TIP:** 3 capsules of blinded TIP at 28 mg dosage strength, inhaled o.d. via the T-326 Inhaler, for 112 days (on treatment).
- **TIP/placebo cyclical:** patients will take the same doses, i.e. 3 capsules o.d., by alternating TIP 28-days with placebo 28-days for 2 cycles for a total of 112 days.
- **Placebo:** The reference product consists of placebo capsules (DSPC/CaCl₂). The dose regimen for the reference product is 3 capsules blinded, inhaled o.d. via the T-326 Inhaler, for 112 days (on treatment).

Cohort B: 5 capsules o.d.

- **TIP:** 5 capsules of blinded TIP at 28 mg dosage strength, inhaled o.d. via the T-326 Inhaler, for 112 days (on treatment).
- **TIP/placebo cyclical:** patients will take the same doses, i.e. 5 capsules o.d., by alternating TIP 28-days with placebo 28-days for 2 cycles for a total of 112 days.
- **Placebo:** The reference product consists of placebo capsules. The dose regimen for the reference product is 5 capsules blinded, inhaled o.d. via the T-326 Inhaler, for 112 days (on treatment).

[figure not shown]
Cohort C: 4 capsules b.i.d.

- **TIP:** 4 capsules of blinded TIP at 28 mg dosage strength, inhaled b.i.d. in the morning and in the evening via the T-326 Inhaler, for 112 days of treatment.
- **TIP/placebo cyclical:** patients will take same doses, i.e. 4 capsules b.i.d., by alternating TIP 28-days with placebo 28-days for 2 cycles for a total of 112 days.

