1.2 Study objectives and endpoints

1.2.1 Primary objectives

- To evaluate the effect of different doses of TIP, administered o.d. or b.i.d., on the change in *P. aeruginosa* bacterial load in sputum as assessed by the change in CFUs from baseline to Day 29 of treatment, each compared to placebo.
- To assess the safety and tolerability with different doses of TIP, administered o.d. or b.i.d., and different regimens (TIP and TIP/placebo cyclical) during the treatment epoch (112 days) and during the follow-up epoch (56 days), each compared to placebo.

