To evaluate the effect of different doses of TIP on the change in P. aeruginosa bacterial load in sputum at Day 29	Change from baseline to Day 29 in P. aeruginosa density in sputum (log ₁₀ CFUs)	Section # 2.5.2
To assess the safety and tolerability with different doses of TIP and different regimens, on treatment epoch and over entire study duration	Safety: incidence rate of AEs/Serious AEs by MedDRA primary SOC and PT terms Tolerability: incidence and severity of local AEs (eg. cough, bronchospasm, dysgeusia, dry mouth, etc.)	2.7.1
Secondary		
To assess the antimicrobial efficacy of TIP over the entire study duration	Change from baseline to each post-baseline visit in P. aeruginosa density in sputum (log ₁₀ CFUs)	2.6.3.1
To assess the effect of different doses of TIP and different regimens on pulmonary exacerbation at the end of treatment epoch (Day 113) and over the study period	Time to first pulmonary exacerbation by exacerbation category Duration of pulmonary exacerbations by exacerbation category Exposure adjusted rate of exacerbations Proportion of patients with at least one pulmonary exacerbation by exacerbation category Proportion of patients who permanently discontinued study drug due to pulmonary	2.6.3.2

[figure not shown]
Objective	Endpoint	Statistical Analysis
To assess the efficacy profile of different doses of TIP and different regimens as measured by anti-pseudomonal antibiotics usage during the treatment epoch (through Day 113) and the study period	exacerbation Time to permanent study drug discontinuation due to pulmonary exacerbation Time to first use (overall, oral, and -parenteral) of anti-pseudomonal antibiotics usage	2.6.3.3
To assess the hospitalization (other than those regularly scheduled hospitalization that were planned prior to study start)	Proportion of patients used anti-pseudomonal antibiotics usage Duration of anti-pseudomonal antibiotics usage Time to first hospitalization due to serious respiratory-related AEs Number of hospitalizations due to serious respiratory-related AEs Proportion of patients requiring hospitalization due to serious respiratory-related AEs	2.6.3.4
To evaluate the safety profile of TIP in terms of clinical laboratory results	Duration of hospitalization due to serious respiratory-related AEs Laboratory results (hematology, serum chemistry, urine dipstick tests): means, mean changes from baseline, frequency/shift tables by visit	2.7.3

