2.7.1 Adverse events (AEs)

An AE will be classified as a treatment emergent AE (TEAE) if it starts on or after the date of the first dose of study drug until study completion.

TEAEs will be summarized by System Organ Class (SOC) and Preferred Term (PT) using the latest Medical Dictionary for Drug Regulatory Affairs (MedDRA) available at the time of database lock.

The number and percentage of patients experiencing TEAEs, SAEs, AEs suspected to be related to study drug, AEs leading to study drug discontinuation and AEs leading to death will be summarized by treatment arm and overall.

The number and percentage of patients experiencing TEAEs will be summarized by treatment arm by SOC and PT, and by SOC, PT and maximum severity. In addition, the number and percentage of patients experiencing AEs suspected to be related to study drug will be summarized by treatment arm by SOC and PT.

For the legal requirements of ClinicalTrials.gov and EudraCT, two required tables on TEAEs which are not serious adverse events with an incidence greater than 5% and on treatment emergent SAEs and SAEs suspected to be related to study treatment will be provided by SOC and PT using the SAF.

If for the same patient, several consecutive AEs (irrespective of study treatment causality, seriousness and severity) occurred with the same SOC and PT:

- a single occurrence will be counted if there is ≤ 1 day gap between the end date of the preceding AE and the start date of the consecutive AE
- more than one occurrence will be counted if there is > 1 day gap between the end date of the preceding AE and the start date of the consecutive AE

For occurrence, the presence of at least one SAE / SAE suspected to be related to study treatment / non SAE has to be checked in a block e.g., among AEs in a ≤ 1 day gap block, if at least one SAE is occurring, then one occurrence is calculated for that SAE.

The number of deaths resulting from SAEs suspected to be related to study treatment and SAEs irrespective of study treatment relationship will be provided by SOC and PT.

AEs of special interest (AESIs):

The number and percentage of patients with AEs regarding ototoxicity and/or hemoptysis and renal events will be summarized. Specific AE terms will be collected on the AESI electronic case report forms (eCRFs). These data include symptoms, medical history and relevant local assessment.

In addition, post-inhalational adverse events will be summarized as instructed 2.7.4.3.

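### SAP 2.7.1 tabulates adverse events over one pooled window, leaving out the by-epoch comparison in the primary safety objective and the protocol's per-cycle summary

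*SAP*

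**What the plan says.** **Objective.** Protocol 2.1 sets the co-primary safety objective "during the treatment epoch (112 days) and during the follow-up epoch (56 days) for each as compared to placebo". SAP 1.2.1 repeats it: "during the treatment epoch (112 days) and during the follow-up epoch (56 days), each compared to placebo". SAP Table 1-1 words the time frame differently, as "on treatment epoch and over entire study duration", gives the incidence and severity of local AEs as the tolerability endpoint, and points to section 2.7.1 for the analysis. A treatment-epoch result is required on either wording.

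**Protocol analysis.** Protocol 9.5.2 defines the window: "AEs will be deemed treatment-emergent if the onset date is on or after the date of first study drug and until study completion". It then asks for a split: "Treatment emergent AEs will be summarized by MedDRA primary SOC and preferred term for each cycle and overall".

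**SAP analysis.** SAP 2.7.1 keeps the protocol's window: an event is treatment-emergent "if it starts on or after the date of the first dose of study drug until study completion". Patients with TEAEs "will be summarized by treatment arm by SOC and PT, and by SOC, PT and maximum severity". The tables for SAEs, related events, events leading to discontinuation and deaths are likewise by arm, with no epoch, cycle or period dimension.

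**Cyclical arms.** SAP 1.1 describes these patients as treated "by alternating TIP 28-days with placebo 28-days for 2 cycles for a total of 112 days", so half of their treatment epoch is on placebo capsules.

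**The concern.** Table 1-1 sends the reader to SAP 2.7.1 for a primary objective stated by epoch, and that section has no output by epoch. A programmer following it would produce one set of tables covering on-drug time, the placebo periods of the cyclical arms, and eight weeks of follow-up with no study drug.

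The trial is meant to support the choice of a tolerable dose and regimen, and Protocol 3.2 defines tolerability by the rate of local AEs. Events tied to inhaling active drug should be looked for mainly while it is being inhaled. A pooled table cannot show whether an excess arose on TIP, on placebo capsules or after treatment ended.

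The SAP does split by period elsewhere. Exacerbation proportions (2.6.3.2) and hospitalizations for serious respiratory AEs (2.6.3.4) are reported for treatment, follow-up and the whole study. Compliance (2.4.1) is split into four visit periods so that the on and off periods of the cyclical arms can be reviewed. The gap in 2.7.1 therefore looks more like an oversight than a decision.

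**Working it through.** **1. The plan's own figure.** Protocol 3.1 gives up to 28 days of screening, 112 of treatment and 56 of follow-up: 28 + 112 + 56 = 196 days, as stated. The post-dose window is 112 + 56 = 168 days.

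**2. Share of the pooled window on each condition**
- Off all study drug, every arm: 56/168 = 33%.
- On TIP, continuous arms: 112/168 = 67%.
- On TIP, cyclical arms: 2 × 28 = 56 days, 56/168 = 33%.

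**3. What a pooled table would show.** The documents give no AE rates, so the on-TIP rate ratio against placebo (RR) is assumed at 1.5, 2 or 3. The background rate is taken as constant, with no carry-over once TIP stops. The time-weighted ratio over the window is

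(RR × TIP days + 1 × other days) / 168.

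For RR = 2: continuous (2 × 112 + 56)/168 = 1.67; cyclical (2 × 56 + 112)/168 = 1.33. Over the treatment epoch alone, cyclical is (2 × 56 + 56)/112 = 1.50.

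| RR on TIP | Continuous, treatment epoch | Continuous, pooled | Cyclical, treatment epoch | Cyclical, pooled |
|---|---|---|---|---|
| 1.5 | 1.50 | 1.33 | 1.25 | 1.17 |
| 2 | 2.00 | 1.67 | 1.50 | 1.33 |
| 3 | 3.00 | 2.33 | 2.00 | 1.67 |

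An epoch split restores the continuous-arm ratio. It does not isolate TIP time in the cyclical arms, which need a split by 28-day period. Nor would a cycle read as 56 days of TIP plus placebo isolate it.

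**4. The same on the scale of the planned tables (patients with an event).** Incidence = 1 − exp(−rate × days). With RR = 2 and an assumed 20% placebo incidence over 112 days:
- Treatment epoch: placebo 20.0%; continuous 1 − 0.8² = 36.0%; difference 16.0 points, ratio 1.80.
- Pooled: placebo 1 − 0.8^1.5 = 28.4%; continuous 1 − 0.8^2.5 = 42.8%; difference 14.3 points, ratio 1.50.

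At 10% placebo incidence the continuous-arm difference moves from 9.0 to 8.5 points, and at 40% from 24.0 to 18.6.

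Part of the fall in the incidence ratio comes only from the longer window. With RR = 2 on all 168 days, incidence would be 1 − 0.8³ = 48.8% and the ratio 48.8/28.4 = 1.72. So 1.80 to 1.72 is window length, and 1.72 to 1.50 is off-drug time. The rate ratios in step 3 do not have this complication.

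**The case against.** **The window is the protocol's own.** This is correct: Protocol 9.5.2 and SAP 2.7.1 define TEAEs identically. The fault lies in the missing split and not in the definition.

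**The objective is partly answered.** A reader might infer that no table answers the primary safety objective. The documents do not support that. The overall tables answer the whole-study half of Table 1-1. Post-inhalation events are planned by visit with an exposure-adjusted rate (Table 1-2), laboratory and audiology results are by visit, respiratory hospitalizations are split by epoch, and AE listings carry the start day relative to first dose. None of these, however, is a by-epoch table of general TEAEs, SAEs or local AEs arising between visits.

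**An undeclared change cannot be shown.** The visible part of SAP section 4 mentions only exacerbation analyses, but the contents page shows a redacted subsection there, and table specifications are in a separate document. What can be said is that the visible SAP does not carry the per-cycle summary over.

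**The regimen comparison is not biased.** A reader might infer that pooling biases continuous against cyclical dosing. It does not. All arms share one window, the placebo periods belong to the cyclical regimen, and the objective compares each regimen with placebo. Fewer events from less active drug is a regimen effect. The pooled table simply cannot describe tolerability while on TIP.

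**Dilution is an assumption.** Protocol 3.2 expects placebo tolerability to be similar to that of TIP, driven largely by the powder inhaled; if so, there is little TIP excess over placebo to dilute. For delayed or persistent events such as ototoxicity, a longer window may capture more of the effect. Both points stand. They limit the size of the effect, but they do not supply the missing epoch comparison.

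**Sparse counts.** With 107 randomized, the planned ratios imply about 107 × 1/3 × 2/5 = 14 patients per TIP arm and 107 × 1/3 × 1/5 = 7 per cohort placebo arm. Full preferred-term tables by severity for every 28-day period would be nearly empty, so the fix should be lighter than that.

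**Conclusion.** The point holds as a gap between a primary objective and its planned output. SAP 2.7.1 as written gives no treatment-epoch or follow-up-epoch comparison of TEAEs, SAEs or local AEs, and the per-cycle summary required by Protocol 9.5.2 is not in its visible text.

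The proportions of time (one third off study drug; TIP on two thirds of days in continuous arms and one third in cyclical arms) come directly from the design. The attenuation does not. It rests on an assumed rate ratio, a constant background rate and no carry-over; under those assumptions an on-TIP ratio of 2 (range 1.5 to 3) reads as 1.67 (1.33 to 2.33) in continuous arms and 1.33 (1.17 to 1.67) in cyclical arms. Differences in percentage points shrink less at low event rates. SAP 2.7 makes safety descriptive only, so no error rate or power is affected. This should be corrected because the objective is primary and the onset dates needed are already collected.

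**What to change.** - Keep the overall first-dose-to-completion tables.
- Add TEAE, SAE and local-AE tables by onset in the treatment epoch and, separately, in the follow-up epoch, by arm and against placebo.
- Add a summary by 28-day period, so that TIP and placebo periods of the cyclical arms stand apart. The four visit periods already defined for compliance in SAP 2.4.1 can serve. Overall incidence and local AEs are enough, given the arm sizes.
- Give exposure-adjusted rates alongside percentages, since the periods differ in length.
- Define cycle in the SAP, because a 56-day cycle would mix TIP and placebo days.
- Assign events to an epoch by the patient's actual last dose and not by a nominal Day 113. Under Protocol 5.6.2, patients who stop treatment early enter follow-up early.
- Align the wording of SAP 1.2.1 and Table 1-1, and record in section 4 any departure from the protocol's per-cycle tables, if it is not already there.

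The cost is additional table runs from existing dates. The drawback is more tables with small counts, to be read descriptively.

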2.7.2 Deaths

AEs leading to death will be listed.

2.7.3 Laboratory data

Laboratory parameters will be recorded at Visit 1 (Screening), Visit 101 (Day 1), Visit 102 (Day 8), Visit 103 (Day 29), Visit 104 (Day 57), Visit 105 (Day 85), Visit 106 or TD (Day 113), Follow-up Visit 201 (Day 141) and Follow-up Visit 202 or PSD (Day 169).

Laboratory data (hematology, serum chemistry), including changes from baseline, will be summarized descriptively (n, mean, SD, median, minimum and maximum).

Hematology

Hematology parameters include hemoglobin, hematocrit, red blood cell (RBC) count, white blood cell (WBC) count with differential, and platelet count.

Serum chemistry

Serum chemistry parameters include urea (or BUN), creatinine, glucose, total bilirubin (TBL), aspartate aminotransferase (AST), alanine aminotransferase (ALT), alkaline phosphatase (ALP), gamma glutamyl transpeptidase, sodium, potassium, chloride, calcium, bicarbonate, phosphate, total protein, albumin, and uric acid.

All continuous laboratory variables will be classified according to the normal ranges (low, normal, high) and shift tables of the categories at baseline versus the last available post-baseline visit will be generated. In addition hematology and serum chemistry value shifts from baseline to above upper/below lower of normal will be tabulated with number and percentage of patients by visit and at any time post-baseline.

Urine dipstick tests

Results of the urine dipstick tests (specific gravity, protein, glucose, blood) will be presented with number and percentage of patients with negative values and trace categories. WBC and RBC sediments result will be summarized in the same manner as described above for continuous laboratory parameters.

Note: a urine pregnancy test will be performed at Visit 2 (Screening 2) and Follow-up Visit 202 or PSD (Day 169). These data will be listed only.

Proportion of patients with liver events at any post-baseline visit

Elevated liver function test cases will be classified according to the following grading system:

- ALT or AST > 3 × upper limit of normal (ULN)
- ALT or AST > 5 × ULN
- ALT or AST > 8 × ULN
- ALT or AST > 10 × ULN
- ALT or AST > 20 × ULN
- ALP > 1.5 × ULN
- ALP > 2 × ULN
- ALP > 5 × ULN
- TBL > ULN
- TBL > 1.5 × ULN
- TBL > 2 × ULN
- ALT or AST > 3 × ULN and TBL > 1.5 × ULN
- ALT or AST > 3 × ULN and TBL > 2 × ULN
- ALT or AST > 3 × ULN and TBL > 2 × ULN without ALP > 2 × ULN

In addition, $3 \times \text{ULN} < \text{ALT} / \text{AST} \leq 5 \times \text{ULN}$ will be evaluated.

For the above mentioned events patient listings will be provided (ALT, AST, TBL, ALP) , by visit, for all visits.

Renal safety

Renal safety will be determined using the following classifications using the central laboratory data provided:

- Serum creatinine increase from baseline 25% - <50%
- Serum creatinine increase from baseline $\geq 50\%$
- BUN increase from baseline $\geq 1.5 \times \text{ULN}$, if it was normal at baseline
- Estimated glomerular filtration rate (eGRF) of 50 mL/min/1.73m² or less
- Dipstick proteinuria $\geq 3+$ (not present at baseline)

- Albumin-creatinine-ratio (ACR) ≥ 30 mg/g or ≥ 3 mg/mmol
- Protein-creatinine-ratio (PCR) ≥ 150 mg/g or ≥ 15 mg/mmol
- Dipstick hematuria $\geq 3+$ (not present at baseline)

For the above mentioned renal safety laboratory parameters, patient listings will be provided (creatinine, eGFR, proteinuria, ACR, PCR), by visit, for all visits.

2.7.4 Other safety data

2.7.4.1 Audiology testing

Audiology testing will be conducted at selected sites at Visit 2 (prior to dosing), Visit 102 (Day 8), Visit 103 (Day 29), Visit 104 (Day 57), Visit 105 (Day 85), Visit 106 or TD (Day 113), Follow-up Visit 201 (Day 141) and Follow-up Visit 202 or PSD (Day 169). Certain patient sub-groups are required to have audiology testing during the screening period.

The results of audiology testing will be summarized at each visit by the number and percentage of patients. Patients with the following decreases in consecutive frequencies will be presented for audiology safety: any frequencies decreased, 2 consecutive frequencies decreased, ≥ 10 dB decrease in ≥ 3 consecutive frequencies, ≥ 15 dB decrease in ≥ 2 consecutive frequencies, ≥ 20 dB decrease in at least 1 frequency. Events can be observed in either ear.

Results of the bone conduction test will be summarized with the number of patients who performed the test; the number and percentage of conductive, neurosensory and mixed hearing loss in left, right or both ears will also be given.

Summaries will be based on the AUD.

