5.6.2 Discontinuation of Study Treatment

Discontinuation of study treatment for a patient occurs when study drug is stopped earlier than the protocol planned duration, and can be initiated by either the patient or the investigator.

The investigator must discontinue study treatment for a given patient if, on balance, he/she believes that continuation would negatively impact the risk/benefit of trial participation.

Study treatment **must** be discontinued under the following circumstances:

- Patient wish
- Non-compliance of the patient with study procedures or investigator instructions, as per the investigator's judgment

- Emergence of AEs when worsened from baseline (Visit 2) or any newly occurring development of AEs with regards to the following:
 - If a patient is found to have a 20-dB or greater decrease in auditory acuity at one or more frequencies in 1 or both ears due to sensorineural deficit, the patient will be withdrawn from treatment and monitored until auditory acuity values return to the most recent pre-dose value (either at screening or baseline) or until study closure, whichever occurs first, i.e. the patient must be withdrawn from study treatment but should continue in the study. In case no pre-dose value is available for comparison, discontinuation of the study treatment and withdrawal of the patient from the study should be based on the investigator's best medical judgment.
- Any of the following laboratory abnormalities when worsened from baseline (Visit 101) or are a newly occurring AE:
 - Proteinuria $\geq 3+$, as confirmed according to Section 14, Appendix 2 Specific Renal Alert Criteria and Actions
 - Serum creatinine increase $\geq 50\%$ compared to baseline, as confirmed according to Section 14, Appendix 2 Specific Renal Alert Criteria and Actions
 - Estimated glomerular filtration rate (GFR) of ≤ 50 mL/min/1.73m²
- Pregnancy (see [Section 6.5.8](#) and [Section 7.6](#))
- Use of any of the prohibited medications detailed in [Table 5-1](#) and [Section 5.5.8](#).
- Any situation in which study participation might result in a safety risk to the patient.

Any renal finding needs to be followed up according to [Section 14 Appendix 2](#) Specific Renal Alert Criteria and Actions, which lists additional laboratory abnormalities that may require study treatment discontinuation based on clinical judgement. Confirmed renal events need to be followed up and documented according to [Section 14 Appendix 2](#).

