To evaluate the audiology safety profile of TIP	Audiology findings (selected centers) by visit	2.7.4.1
To evaluate the safety profile of TIP in terms of bronchial hyperreactivity	visit Acute change in FEV ₁ % predicted values from pre-dose to 30±15 minutes after completion of study drug administration at the clinical site at visits during the treatment epoch	2.7.4.4
To evaluate the treatment effect of TIP on the Respiratory Symptom Scale Quality of Life Questionnaire for Bronchiectasis (QOL-B)	Change from baseline to all post-baseline visits	2.10
Pharmacokinetic concentrations of tobramycin in serum and in sputum	Concentration data at scheduled visits and timepoints	2.8

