2.1.1 General definitions

Study drug is defined as any single dose of TIP or placebo administered to the patient as part of the required study procedures.

The date of first dose of study drug is defined as the date of first administration of TIP or placebo; the date of last dose of study drug is defined as the date of the last administration of TIP or placebo.

For dates on or after the date of first dose of study drug, study day is defined as [date of interest – date of first dose of study drug] + 1. For dates before the date of first dose of study drug, study day is defined as [date of first study drug – date of interest].

For each visit, the date recorded by the investigators in the eCRF (variable SVSTDTC in the SDTM SV dataset) will be considered as the visit date in all the algorithms and the listings.

In general, the nominal visits will be used for the by visits summaries. However, for early treatment discontinued patients, data collected at end of treatment (EOT) visit will be mapped to next planned visits after their last scheduled visits before the discontinuation.

Baseline is defined as the last non-missing result prior to the first administration of study drug.

End/last date of study for each patient is defined by the date of last contact as recorded in the database.

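### The audiometric decrease criteria are tabulated only visit by visit, so no planned table gives the per-patient incidence of measured hearing loss over the treatment epoch; one added table would supply it

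*SAP*

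**What the plan says.** SAP 2.7.4.1 sets the unit of the audiometry tables: "The results of audiology testing will be summarized at each visit by the number and percentage of patients". It then lists five graded criteria, introduced by "Patients with the following decreases in consecutive frequencies will be presented for audiology safety". They run from any decrease up to a loss of at least 20 dB at one frequency. SAP Table 1-1 gives the endpoint as "Audiology findings (selected centers) by visit", and protocol 9.5.2 agrees: "Audiology function data will be analyzed via summary statistics by treatment and visit".

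The objective itself covers a period. Protocol 2.2 and SAP 1.2.2 both ask about audiology findings across the whole treatment epoch.

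On a sensorineural drop of 20 dB or more, protocol 5.6.2 says "the patient will be withdrawn from treatment and monitored until auditory acuity values return to the most recent pre-dose value", and adds that "the patient must be withdrawn from study treatment but should continue in the study". The same section sends patients who stop treatment to a discontinuation (TD) visit and then into follow-up.

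SAP 2.1.1 says "In general, the nominal visits will be used for the by visits summaries", and maps data from the end-of-treatment visit of an early discontinuer to the next planned visit. For laboratory shifts, SAP 2.7.3 does more: they are "tabulated with number and percentage of patients by visit and at any time post-baseline". Liver events are also counted at any post-baseline visit.

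**The concern.** Ototoxicity is a recognised aminoglycoside risk, and comparing safety across doses and regimens is a primary objective. The natural question is how many patients in each arm had a measured hearing loss while on treatment. The planned tables answer a different one: of those tested at a given visit, how many met the criterion then.

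The two answers diverge most for the 20 dB criterion, because meeting it removes the patient from later treatment visits. A reader who takes the Day 113 row as the end-of-treatment result would see a figure from which earlier cases have gone, and an arm with more early cases would lose more of them.

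**Working it through.** The documents give no audiometric rate, so there is no planned figure to reproduce. The check follows a patient through the rules and then illustrates the size.

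**Path of a patient with a 20 dB loss.**
1. The loss is found at a scheduled visit and counted in that row.
2. Treatment stops and a TD visit takes place. If the detection visit serves as the TD visit, the patient appears in one treatment row. If a separate TD visit follows, SAP 2.1.1 maps it to the next planned visit and the patient can appear in two.
3. The patient enters follow-up and is absent from the remaining treatment rows. SAP 2.1 bases percentages on non-missing values, so the patient leaves the denominator too.

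**Illustration for treatment rows.** Assumptions: four on-treatment audiograms (Visits 103 to 106, protocol 6.5.7), equal risk h in each interval, no other drop-out, and a loss still present at TD. For cumulative incidence C:

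- h = 1 − (1 − C)^(1/4)
- Day 113 row, one appearance per case: h
- Day 113 row, separate TD visit mapped forward: 1 − (1 − h)² = 1 − (1 − C)^(1/2)

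| Assumed C | Day 113, one appearance | Day 113, with mapped TD |
|---|---|---|
| 8% | 2.1% | 4.1% |
| 12% | 3.1% | 6.2% |
| 20% | 5.4% | 10.6% |

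**Does adding the rows recover C?** Take C = 12%, with a fixed denominator of all tested patients. New cases at the four visits are h, h(1−h), h(1−h)² and h(1−h)³, that is 3.15 + 3.05 + 2.95 + 2.86 = 12.0%. With one appearance each, the sum is right. If the first three groups appear again through a mapped TD audiogram, the sum is 12.0 + 3.15 + 3.05 + 2.95 = 21.1%. The tables do not show which case applies.

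**Other criteria.** The 10 dB and 15 dB criteria do not themselves stop treatment. A patient meeting only one of these can be counted at every visit where it persists, so a sum of rows overcounts.

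**Follow-up rows.** Protocol 6.5.7 repeats abnormal audiology at all later visits but needs no test at Visits 201 and 202 when audiology was normal through Visit 106. Rows based on those tested are then enriched for affected patients.

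**Unscheduled tests.** Protocol 6.5.7 sends any patient who suspects a hearing change to an audiologist, whether or not the site is in the audiology sub-study. The SAP does not say how such audiograms enter tables built on nominal visits. The audiology population in SAP 2.2 requires one test, not a pre-dose one, so the denominator for a change is not defined.

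**Arm size.** SAP 1 gives 107 randomised patients. Each active arm holds about 107 × 2/15 = 14, and fewer have routine audiometry because it is done at selected sites. Three affected patients in such an arm (3/14 = 21%) could show as none or one at a given visit.

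**The case against.** The strongest reply is that the cases are not lost. Each is counted at the visit where it is found, and if it appears once, the rows add up to the full total, as shown above. Setting 3.1% against 12% compares one row with a cumulative figure. This stands as a limit on what the illustration proves. It does not remove the gap, because the tables do not reveal whether a patient appears once or more.

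Second, patient-level outputs do exist. SAP 2.7.1 counts patients with ototoxicity adverse events of special interest. SAP 2.7.4.1 counts patients who had bone-conduction testing, which protocol 6.5.7 triggers on a 20 dB air-conduction drop. Protocol 5.6.2 also lists that drop under emerging adverse events, so many such cases should be reported as events. It would therefore be wrong to infer that the trial reports no per-patient measure of ototoxicity. What remains is partial: under protocol 7.1 an asymptomatic change of 10 or 15 dB need not become an adverse event, and bone conduction serves one criterion only.

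Third, SAP 2.7.4.1 labels the Day 113 visit as Visit 106 or TD. If TD audiograms were shown in that row, it would keep the withdrawn patients and most of the depletion would vanish. SAP 2.1.1 points the other way, and the SAP does not say which governs here.

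Finally, table specifications sit in a separate document that might contain an any-time row, the safety analysis is descriptive, and listings show every result. All true, but the analysis plan should state the summary that its own objective needs.

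**Conclusion.** The gap is real and modest. As written, no planned table gives per-patient audiometric incidence over the treatment epoch for any of the decrease criteria. For the 20 dB criterion, late treatment-visit percentages read as incidence are too low under the mapping rule in SAP 2.1.1. Follow-up percentages may be too high.

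A reader might infer that the plan understates ototoxicity as a whole, or that its tables show only a quarter to a half of affected patients. The documents support neither. Cases appear where they are detected, errors can run in both directions, only the 20 dB rule forces withdrawal, and adverse event reporting captures part of the picture. The 8% to 20% range is illustrative, and the calculated figures rest on equal interval risk and no other drop-out.

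**What to change.** In SAP 2.7.4.1, keep the visit tables and add one table. For each decrease criterion it gives the number and percentage of patients meeting it at any post-baseline audiogram (scheduled, TD or unscheduled), through Day 113 and through Day 169, by cohort and arm. The denominator is patients with a pre-dose and at least one post-baseline audiogram. Show event-driven tests separately, and list patients without a pre-dose audiogram, since complaint-driven tests at sites outside the sub-study will often lack one. State which row receives the TD audiogram.

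The audiology visit lists should also be reconciled: SAP 2.7.4.1 includes Visit 102 and protocol 6.5.7 does not.

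The cost is a short addition to the text and one table from data already collected. The any-time count will also pick up transient test-retest changes, which the retained visit tables and listings help to identify. No clinical rule is affected.
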